4.1.2.6 Management of stomatitis / oral mucositis / mouth ulcers

Adverse Drug Reaction	Severity	Everolimus Dose Adjustment and Management Recommendations
Stomatitis	Grade 1 (Minimal symptoms, normal diet)	No dose adjustment required. Manage with non-alcoholic or salt water (0.9%) mouth wash several times a day.
	Grade 2 (Symptomatic but can eat and swallow modified diet)	Temporary dose interruption until recovery to grade ≤ 1 . Re-initiate everolimus at the same dose. If stomatitis recurs at grade 2, interrupt dose until recovery to grade ≤ 1 . Re-initiate everolimus at one dose level lower. Manage with topical analgesic mouth treatments (e.g. benzocaine, butyl aminobenzoate, tetracaine hydrochloride, menthol or phenol) with or without topical corticosteroids (i.e. triamcinolone oral paste)*.
	Grade 3 (Symptomatic and unable to adequately eat or hydrate orally)	Temporary dose interruption until recovery to grade ≤ 1 . Re-initiate everolimus at one dose level lower. Manage with topical analgesic mouth treatments (i.e. benzocaine, butyl aminobenzoate, tetracaine hydrochloride, menthol or phenol) with or without topical corticosteroids (i.e. triamcinolone oral paste)*
	Grade 4 (Symptoms associated with life-threatening consequences)	Discontinue everolimus and treat with appropriate medical therapy.

* using agents containing alcohol, hydrogen peroxide, iodine, and thyme derivatives in management of stomatitis as they may worsen mouth ulcers.

Patients with a clinical history of stomatitis/mucositis/mouth ulcers and those with gastrointestinal morbidity associated with mouth/dental infections, irritation of esophageal mucosa e.g. gastroesophageal reflux disease (GERD) and pre-existing stomatitis/mucositis must be monitored even more closely. Patients should be instructed to report the first onset of buccal mucosa irritation/reddening to their study physician immediately.

Stomatitis/oral mucositis/mouth ulcers due to everolimus should be treated using local supportive care. Please note that investigators in earlier trials have described the oral toxicities associated with everolimus as mouth ulcers, rather than mucositis or stomatitis. If your examination reveals mouth ulcers rather than a more general inflammation of the mouth, please classify the adverse event as such. The suggested paradigm for treatment of stomatitis/oral mucositis/mouth ulcers is as follows:

1. For mild toxicity (grade 1), no dose adjustment required. Manage with non-alcoholic mouth wash or salt water (0.9%) mouth wash several times a day until resolution.
2. For more severe toxicity (grade 2 in which case patients have pain but are able to maintain adequate oral alimentation, or grade 3 in which case patients cannot maintain adequate oral

alimentation), the suggested treatments are topical analgesic mouth treatments (i.e., local anesthetics such as, benzocaine, butyl aminobenzoate, tetracaine hydrochloride, menthol, or phenol) with or without topical corticosteroids, such as triamcinolone oral paste 0.1% (Kenalog in Orabase®).

3. Agents containing alcohol, hydrogen peroxide, iodine, and thyme derivatives may tend to worsen mouth ulcers. These agents should be avoided.
4. Antifungal agents should be avoided unless a fungal infection is diagnosed. In particular, systemic imidazole antifungal agents (ketoconazole, fluconazole, itraconazole, etc.) should be avoided in all patients due to their strong inhibition of everolimus metabolism, therefore leading to higher everolimus exposures. Therefore, topical antifungal agents are preferred if an infection is diagnosed.

4.1.2.7 Management of diarrhea

Appearance of grade 1-2 diarrhea attributed to study drug toxicity may be treated with supportive care such as loperamide, initiated at the earliest onset (for example 4 mg orally followed by 2 mg orally every 2 hours until resolution of diarrhea).

4.1.2.8 Management of hyperlipidemia and hyperglycemia

Adverse Drug Reaction	Severity	Everolimus Dose Adjustment and Management Recommendations
Metabolic events (e.g. hyperglycemia, dyslipidemia)	Grade 1	No dose adjustment required. Initiate appropriate medical therapy and monitor.
	Grade 2	No dose adjustment required. Manage with appropriate medical therapy and monitor.
	Grade 3	Temporary dose interruption. Re-initiate everolimus at one dose level lower. Manage with appropriate medical therapy and monitor.
	Grade 4	Discontinue everolimus and treat with appropriate medical therapy.

Treatment of hyperlipidemia should take into account the pre-treatment status and dietary habits of the patient. Grade 2 or higher hypercholesterolemia (>300 mg/dL or 7.75 mmol/L) or grade 2 hypertriglyceridemia or higher (>2.5x upper normal limit) should be treated with a 3-hydroxy-3-methyl-glutaryl (HMG)-CoA reductase inhibitor (e.g. atorvastatin, pravastatin, fluvastatin) or appropriate triglyceride-lowering medication, in addition to diet.

Note: Concomitant therapy with fibrates and an HMG-CoA reductase inhibitor is associated with an increased risk of a rare but serious skeletal muscle toxicity manifested by rhabdomyolysis, markedly elevated creatine phosphokinase (CPK) levels and myoglobinuria, acute renal failure and sometimes death. The risk versus benefit of using this therapy should be determined for individual patients based on their risk of cardiovascular complications of hyperlipidemia.

Dyslipidemia (including hypercholesterolemia and hypertriglyceridemia) has been reported in patients taking everolimus. Monitoring of blood cholesterol and triglycerides prior to the start of everolimus therapy and periodically thereafter as well as management with appropriate medical therapy is recommended.

Hyperglycemia has been reported in patients taking everolimus. Monitoring of fasting serum glucose is recommended prior to the start of everolimus and periodically thereafter. More frequent monitoring is recommended when everolimus is co-administered with other drugs that may induce hyperglycemia. Optimal glycemic control should be achieved before starting a patient on everolimus.

4.1.2.9 Management of non-infectious pneumonitis

Non-infectious pneumonitis is a class effect of rapamycin derivatives. Cases of non-infectious pneumonitis (including interstitial lung disease) have also been described in patients taking everolimus. Some of these have been severe and on rare occasions, a fatal outcome was observed.

- A diagnosis of non-infectious pneumonitis should be considered in patients presenting with non-specific respiratory signs and symptoms such as hypoxia, pleural effusion, cough or dyspnea, and in whom infectious, neoplastic and other non-medicinal causes have been excluded by means of appropriate investigations. Opportunistic infections such as PJP should be ruled out in the differential diagnosis of non-infectious pneumonitis. Patients should be advised to report promptly any new or worsening respiratory symptoms.

Patients who develop radiological changes suggestive of non-infectious pneumonitis and have few or no symptoms may continue everolimus therapy without dose alteration.

If symptoms are moderate (grade 2), consideration should be given to interruption of therapy until symptoms improve. The use of corticosteroids may be indicated. Everolimus may be reintroduced at a daily dose approximately 50% lower than the dose previously administered.

For cases of grade 3 non-infectious pneumonitis, interrupt everolimus until resolution to less than or equal to grade 1. Everolimus may be re-initiated at a daily dose approximately 50% lower than the dose previously administered depending on the individual clinical circumstances. If toxicity recurs at grade 3, consider discontinuation of everolimus. For cases of grade 4 non-infectious pneumonitis, everolimus therapy should be discontinued. Corticosteroids may be indicated until clinical symptoms resolve.

For patients who require use of corticosteroids for treatment of non-infectious pneumonitis, prophylaxis for pneumocystis jirovecii pneumonia (PJP) may be considered. The two compounds studied most extensively for prophylaxis against PJP have been trimethoprim-sulfamethoxazole, given orally, and pentamidine, given as an aerosol.

If non-infectious pneumonitis develops, the guidelines should be followed. Consultation with a pulmonologist is recommended for any case of pneumonitis that develops during the study.

Management of non-infectious pneumonitis

Worst grade pneumonitis	Suggested investigations	Management of pneumonitis	Everolimus dose adjustment
Grade 1 (Asymptomatic, radiographic findings only)	CT scans with lung windows.	No specific therapy is required	No dose adjustment required. Initiate appropriate monitoring.
Grade 2 (Symptomatic, not interfering with Activities of Daily Living)	CT scan with lung windows. Consider pulmonary function testing includes: spirometry, DLCO, and room air O ₂ saturation at rest. Consider a bronchoscopy with biopsy and/or BAL. Monitoring at each visit until return to ≤ grade 1. Return to initial monitoring frequency if no recurrence.	Symptomatic only. Consider corticosteroids and/or other supportive therapy if symptoms are troublesome.	Rule out infection and consider interruption of everolimus until symptoms improve to Grade ≤ 1. Re-initiate everolimus at one dose level lower. Discontinue everolimus if failure to recover within ≤ 28 days.
Grade 3 (Symptomatic, Interfering with Activities of Daily Living. O ₂ indicated)	CT scan with lung windows and pulmonary function testing includes: spirometry, DLCO, and room air O ₂ saturation at rest. Monitoring at each visit until return to ≤ grade 1. Return to initial monitoring frequency if no recurrence. Bronchoscopy with biopsy and/or BAL is recommended.	Consider corticosteroids if infective origin is ruled out. Taper as medically indicated.	Rule out infection and interrupt everolimus until symptoms improve to Grade ≤ 1. Consider re-initiating everolimus at one dose level lower. Discontinue everolimus if failure to recover within ≤ 28 days. If toxicity recurs at Grade 3, consider discontinuation
Grade 4 (Life-threatening, ventilatory support indicated)	CT scan with lung windows and required pulmonary function testing, if possible, includes: spirometry, DLCO, and room air O ₂ saturation at rest. Monitoring at each visit until return to ≤ grade 1. Return to initial monitoring frequency if no recurrence. Bronchoscopy with biopsy and/or BAL is recommended if possible.	Consider corticosteroids if infective origin is ruled out. Taper as medically indicated.	Rule out infection and discontinue everolimus.

4.1.2.10 Management of hepatitis reactivation / flare

Reactivation of Hepatitis B (HBV) has been observed in patients with cancer receiving chemotherapy[98]. Sporadic cases of Hepatitis B reactivation have also been seen in this setting with everolimus. Use of antivirals during anti-cancer therapy has been shown to reduce the risk of Hepatitis B virus reactivation and associated morbidity and mortality[99]. A detailed assessment of Hepatitis B/C medical history and risk factors must be done for all patients at baseline, with testing performed prior to the first dose of study drug.

Monitoring and prophylactic treatment for hepatitis B reactivation

Table 11 provides detail of monitoring and prophylactic therapy according to the baseline results of viral load and serologic markers testing.

Table 11 Action to be taken based on screening hepatitis B results

Test	Result	Result	Result	Result	Result
HBV-DNA	+	+ or -	-	-	-
HBsAg	+ or -	+	-	-	-
HBsAb	+ or -	+ or -	+ and no prior HBV vaccination	+ or -	- or + with prior HBV vaccination
HBcAb	+ or -	+ or -	+ or -	+	-
Recommendation	Prophylaxis treatment should be started 1-2 weeks prior to first dose of everolimus Monitor HBV-DNA approximately every 4-8 weeks		No prophylaxis Monitor HBV-DNA approximately every 3-4 weeks		No specific action

Antiviral prophylaxis therapy should continue for at least 4 weeks after last dose of everolimus. For HBV reactivation definition and management guidelines, see **Table 12**.

Table 12 Guidelines for the management of hepatitis B reactivation

HBV reactivation (with or without clinical signs and symptoms)*	

For patients with baseline results: Positive HBV-DNA OR positive HBsAg ----- ---- reactivation is defined as: [Increase of 1 log in HBV-DNA relative to baseline HBV-DNA value OR new appearance of measurable HBV-DNA]
	
Treat: Start a second antiviral medication AND Interrupt everolimus administration until resolution:
 
 • ≤ baseline HBV-DNA levels 
If resolution occurs within ≤ 28 days, everolimus should be re-started at one dose lower, if available. (see Table 7 for dose levels available) If the patient is already receiving the lowest dose of everolimus according to the protocol, the patient should restart at the same dose after resolution. Both antiviral therapies should continue at least 4 weeks after last dose of everolimus.
 
If resolution occurs > 28 days Patients should discontinue everolimus but continue both antiviral therapies at least 4 weeks after last dose of everolimus.

For patients with baseline results: Negative HBV-DNA and HBsAg AND [Positive HBsAb (with no prior history of vaccination against HBV), OR positive HBcAb] ----- --- Reactivation is defined as: New appearance of measurable HBV-DNA
	
Treat: Start first antiviral medication AND Interrupt everolimus administration until resolution:
 
 • ≤ undetectable (negative) HBV-DNA levels 
If resolution occurs within ≤ 28 days, everolimus should be re-started at one dose lower, if available (see Table 7 for dose levels available). If the patient is already receiving the lowest dose of everolimus according to the protocol, the patient should restart at the same dose after resolution. Antiviral therapy should continue at least 4 weeks after last dose of everolimus.
 
If resolution occurs > 28 days Patients should discontinue everolimus but continue antiviral therapy at least 4 weeks after last dose of everolimus.

* All reactivations of HBV are to be recorded as grade 3 (e.g. CTCAE Version 4.0 - Investigations/Other: Viral Reactivation), unless considered life threatening by the investigator, in which case they should be recorded as grade 4. Date of viral reactivation is the date on which the rise or reappearance of HBV-DNA was recorded.

Monitoring for hepatitis C flare

The following two categories of patients should be monitored every 4–8 weeks for HCV flare:

- Patients with detectable HCV RNA-PCR test at screening.
- Patients known to have a history of HCV infection, despite a negative viral load test at screening (including those that were treated and are considered ‘cured’)

For definitions of HCV flare and actions to be taken in the event of a flare, please refer to **Table 13**.

Table 13 Guidelines for the management of hepatitis C flare

Baseline results	HCV flare definition*	HCV flare management
Detectable HCV-RNA	> 2 log ₁₀ IU/mL increase in HCV-RNA AND ALT elevation > 5 x ULN or 3 x baseline level, whichever is higher.	Discontinue everolimus
Knowledge of past hepatitis C infection with no detectable HCV-RNA	New appearance of detectable HCV-RNA AND ALT elevation > 5 x ULN or 3 x baseline level, whichever is higher.	Discontinue everolimus

* All flares of HCV are to be recorded as grade 3 (e.g. CTCAE Version 4.0 - Investigations - Other: Viral Flare), unless considered life threatening by the investigator; in which case, they should be recorded as grade 4. Date of viral flare is the date on which both the clinical criteria described above were met. (e.g., for a patient whose HCV-RNA increased by 2 logs on 01 JAN 2011 and whose ALT reached > 5 x ULN on 22 JAN 2011, the date of viral flare is 22 JAN 2011).

4.2 CONCURRENT MEDICATIONS

4.2.1 General guidelines

Patients must be instructed not to take any medications (over-the-counter or other products) during the protocol treatment period without prior consultation with the investigator. The investigator should instruct the patient to notify the study site about any new medications he/she takes after the start of study drug. All medications (other than study drug) and significant non-drug therapies (including physical therapy and blood transfusions) taken within 28 days of starting study treatment through the 30-day safety follow up visit should be reported on the CRF.

4.2.2 Cytochrome P450 and P-glycoprotein inhibitors/inducers/substrates

Co-administration of everolimus or sunitinib with strong inhibitors of CYP3A4 or PgP should be avoided; and may cause increased drug concentrations. For a current table of Substrates, Inhibitors and Inducers please access the following website:

<http://www.fda.gov/Drugs/DevelopmentApprovalProcess/DevelopmentResources/DrugInteractionsLabeling/ucm093664.htm>

Everolimus is metabolized by CYP3A4 in the liver and to some extent in the intestinal wall.

Therefore, the following are recommended:

- Co-administration with strong inhibitors of CYP3A4 (e.g., ketoconazole, itraconazole, ritonavir) or P-glycoprotein (PgP) inhibitor should be avoided.
- Co-administration of either study drug with moderate CYP3A4 inhibitors (e.g., erythromycin, fluconazole) or PgP inhibitors should be used with caution. If a patient requires co-administration of moderate CYP3A4 inhibitors or PgP inhibitors, reduce the dose of everolimus by approximately 50%. Additional dose reductions to every other day may be required to manage toxicities. If the inhibitor is discontinued, the everolimus dose should be returned to the dose used prior to initiation of the moderate CYP3A4/PgP inhibitor after a washout period of 2 to 3 days.

- Grapefruit, Seville oranges, and starfruit affect P450 and PgP activity. Concomitant use should be avoided.
- If patients require co-administration of a strong CYP3A4 inducer with everolimus, consider doubling the daily dose of everolimus (based on pharmacokinetic data), using increments of 5 mg or less. This dose of everolimus is predicted to adjust the AUC to the range observed without inducers. However, there are no clinical data with this dose adjustment in patients receiving strong CYP3A4 inducers. If the strong inducer is discontinued, consider a washout period of at least 3 to 5 days (reasonable time for significant enzyme de-induction), before the everolimus dose is returned to the dose used prior to initiation of the strong CYP3A4 inducer.
- This dose adjustment of everolimus is intended to achieve similar AUC to the range observed without inducers. However, there are no clinical data with this dose adjustment in patients receiving strong CYP3A4 inducers. If the strong inducer is discontinued the everolimus dose should be returned to the dose used prior to initiation of the strong CYP3A4/PgP inducer.

Please refer to **Table 14** listing relevant inducers and inhibitors of CYP3A and **Table 15** for a list of relevant substrates, inducers, and inhibitors of PgP.

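### For rifampin and St John's wort, section 4.2.2 with Tables 14 and 15 gives opposing everolimus dose instructions and does not say which governs

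*Combined protocol and SAP*

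**What the plan says.** Section 4.2.2 sets the everolimus dose rules for interacting drugs and refers the reader to Tables 14 and 15 in section 4.2.2.1 to classify each drug.

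- **Strong CYP3A4 inducers.** "If patients require co-administration of a strong CYP3A4 inducer with everolimus, consider doubling the daily dose of everolimus", "using increments of 5 mg or less". The stated aim is exposure: "This dose of everolimus is predicted to adjust the AUC to the range observed without inducers". On stopping the inducer, "consider a washout period of at least 3 to 5 days" before going back to the previous dose.
- **PgP inhibitors.** The first bullet says that a strong CYP3A4 inhibitor "or P-glycoprotein (PgP) inhibitor should be avoided". The next bullet covers the case where one is needed: "If a patient requires co-administration of moderate CYP3A4 inhibitors or PgP inhibitors, reduce the dose of everolimus by approximately 50" percent. On stopping, the dose goes back "after a washout period of 2 to 3 days".
- **Table 14** lists rifampin and St John's wort among the strong CYP3A inducers.
- **Table 15** lists the same two drugs twice: as the only entries in its Inducers row, and again in the row for PgP inhibitors and dual PgP/CYP3A inhibitors.
- **Section 11.2.9** gives rifampin as an example of a strong CYP3A4 inducer, advises against such drugs unless everolimus trough levels are closely monitored, and refers back to section 4.2.2.

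**The concern.** An investigator who looks up either drug finds it under two headings, and the headings carry opposite dose changes. Section 4.2.1 sends every new medication, including over-the-counter products, through the investigator, so this lookup is how the dose would be decided.

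If the inhibitor entry is followed, everolimus is halved alongside a drug that the same protocol grades as a strong inducer. The protocol's own prediction is that doubling brings exposure back to the level seen without an inducer, so halving moves the dose away from that target. The risk is underdosing of a cancer drug by following a written instruction. It is not confined to Arm 2, because patients who cross over from sunitinib also receive everolimus (section 3.1.1).

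**Working it through.** The plan gives no statistical figure on this point. The check is a comparison of the tables and rules, plus simple dose arithmetic.

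**1. Which drugs are affected**

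- Strong inducers in Table 14: 8 (avasimibe, carbamazepine, mitotane, phenobarbital, phenytoin, rifabutin, rifampin, St John's wort).
- Drugs in the Table 15 inhibitor row: 39.
- Drugs on both lists: 2, rifampin and St John's wort.

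Table 14 inducers of any grade that also stand in the Table 15 inhibitor row number 6. The other 6 − 2 = 4 are ritonavir and tipranavir (moderate inducers) and ginkgo and telaprevir (weak inducers). Section 4.2.2 has no inducer dose rule for moderate or weak inducers, so no opposing instruction arises for these four. The conflict is confined to two drugs.

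**2. The two instructions side by side, from the 10 mg starting dose in section 3.2.2**

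| | Read as strong inducer (Table 14) | Read as PgP inhibitor (Table 15) |
|---|---|---|
| Default | Not recommended without trough monitoring (11.2.9, which names rifampin only) | Avoid |
| Dose if required | Consider doubling: 10 × 2 = 20 mg, reached in (20 − 10) / 5 = 2 steps of 5 mg; 10 mg if doubling is considered and not done | Reduce by about half: 10 × 0.5 = 5 mg |
| On stopping | Consider at least 3 to 5 days of washout | 2 to 3 days of washout |

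The ratio between the two readings is 10 / 5 = 2 without doubling and 20 / 5 = 4 with full doubling.

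**3. Whether any text sets precedence**

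- Sections 4.2.2 and 4.2.2.1 contain no rule for a drug listed as both inducer and inhibitor.
- Exclusion criterion 2.1.2.17 concerns strong inhibitors only and does not mention inducers. Table 15 does not grade its PgP inhibitors by strength.
- Section 11.2.9 supports the inducer reading for rifampin. It omits St John's wort, states no dose, and points back to section 4.2.2.
- The web link in section 4.2.2 leads to an outside table and is not a precedence rule in the protocol.

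No text resolves the conflict for St John's wort, and for rifampin the documents give only an indication.

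**The case against.** The best counter-argument is that the protocol mostly points one way. Section 4.2.2 introduces its recommendations with CYP3A4 metabolism, Table 14 grades both drugs as strong inducers, and section 11.2.9 names rifampin as one. Both dose rules apply only when the patient requires the drug, and for rifampin the default is similar under either reading: avoid it, or do not use it without monitoring. A pharmacist may well choose correctly. All of this stands and keeps the point small. It does not supply the missing rule, and it says least about St John's wort.

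A reader might infer more than the documents support, in three ways.

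- *That the inhibitor-row entries are factually wrong and should be deleted.* Table 15 cites an internal interaction memo that is not available here, so the documents cannot show this. The wording in "If the strong inducer is discontinued the everolimus dose should be returned to the dose used prior to initiation of the strong CYP3A4/PgP inducer" does not settle it either. In the parallel inhibitor bullet the same slash refers back to drugs of one kind or the other, so the phrase need not single out drugs that induce both CYP3A4 and PgP.
- *That the second inducer bullet sets a third stopping rule with no washout.* That bullet continues the first and is silent on washout. Silence does not set the washout to none.
- *That the dose gap is 4-fold.* That figure needs full doubling, which is discretionary.

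**Conclusion.** The conflict is real and limited to rifampin and St John's wort. From 10 mg daily, one reading gives about 5 mg and the other 10 to 20 mg. The difference is 2-fold if doubling is considered and not done, and up to 4-fold if it is done. The recommended washouts also differ: at least 3 to 5 days (to be considered) against 2 to 3 days.

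The conclusion assumes that a patient on everolimus requires one of these drugs and that the investigator relies on the tables. The documents give no rate of use for either drug, so the number of patients affected is unknown and probably small. This is a minor dosing-safety correction. The documents do not support extending it to the statistical design: power, alpha and the PFS analysis are unaffected.

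**What to change.** Footnote rifampin and St John's wort in the Table 15 inhibitor row, and add one sentence to the first inducer bullet of section 4.2.2: *For everolimus dosing, rifampin and St John's wort are handled only under the strong-inducer rule; strong inducers are not recommended without the trough monitoring in 11.2.9.* The table entries can stay, since the footnote removes the ambiguity without a judgement on their source.

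Optionally, merge the second inducer bullet into the first and keep the 3 to 5 day washout. The rules for moderate CYP3A4 inhibitors and the fluconazole precaution in section 4.1.2.6 should be left alone. Rewording them would change clinical policy, and this conflict does not require it.

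The cost is wording in one amendment, with no added patients or visits. Trough monitoring is already asked for in section 11.2.9. The study calendar (section 3.4) schedules no everolimus trough sample, so it would be arranged case by case. The documents give no trough target and none is proposed here.
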